# 3.3. Comparison of treatment strategies

See Table 2 below for a proposed presentation of primary and secondary endpoints.

Main analyses will be performed on an intention-to-treat (ITT) basis, with inclusion of all randomised patients in the analysis according to the treatment group they were initially allocated. Analyses will also be done per-protocol (PP), including participants who met the inclusion criteria and received the assigned treatment. During trial monitoring is has become apparent that, for some cases, vertebral stenosis of at least 50% has not been confirmed on central imaging review.

The per-protocol analysis will include:

- 1. Patients with symptomatic vertebral stenosis from presumed atheromatous disease
- 2. Patients in whom central imaging review confirmed vertebral stenosis of ≥50%
- 3. Patients who received the allocated treatment

ITT and PP analyses will be performed for the primary and secondary endpoints, which are listed below. Not all secondary endpoints may be reported in the published article but the following analyses will be presented in the study plan;

Primary endpoint:

• Fatal and non-fatal stroke in any arterial territory during trial follow-up

Secondary endpoints:

- Fatal or non-fatal stroke in any arterial territory at 3 months post-randomisation
- Posterior circulation stroke (including periprocedural stroke) during follow-up
- Periprocedural stroke or death (within 30 days of procedure)
- Posterior circulation stroke and TIA during follow-up
- Any disabling stroke (defined by a Modified Rankin score ≥3) during follow-up
- Death of any cause during follow-up
- Restenosis (stenosis >50% in the treated artery) in treated artery during follow-up
- NHS and personal social services costs (UK patients only)\*
- Quality-adjusted life years\*
- Within-trial and long-run incremental cost-effectiveness\*

\*As specified in the protocol (pages 12-13).

The main analyses will be repeated for intracranial and extracranial strokes separately.

The intensity of medical treatment will be compared between the two groups over the first 30 days and over the full trial duration by assessing presence/absence and number of the following treatments: anti-platelets; statins; antihypertensives. Blood pressure measurements during follow-up in the two groups will be compared. Treatment of diabetes mellitus and current smoking will be recorded.

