In analyses of primary and secondary endpoint events at 3 months post-randomisation and during complete follow-up, follow-up will start immediately after randomisation. Follow-up will range from 1 year for the last recruited patients to about 7.5 years for first recruited patients. If the event numbers are sufficient, hazard ratios with 95% confidence intervals will be estimated by using Cox proportional hazards regression models, with patients censored at the time of first event of each type, death, last contact date, or the end of follow-up. The proportional hazards assumption for the treatment will be tested using Schoenfeld residuals. Kaplan-Meier survival analysis will be used to construct time-to-event curves, and the log-rank test will be used to evaluate whether there is a statistical significance difference in the cumulative risk of stroke between the two treatment groups.

We will also analyse short term outcomes to assess the operative risk. For this we have chosen a 30 day follow-up period but this may be adjusted before unblinding to results and analysis if we find stenting has not been carried out by 30 days in a significant number of individuals. For 30-days events, follow-up for each patient will start immediately after recruitment for patients allocated medical treatment alone and immediately after the stenting procedure for patients allocated stenting. If stenting was not performed in a patient allocated stenting, follow-up will begin directly after randomisation. The proportions of outcome events within 30-days of treatment will be compared with exact logistic regression to estimate odds ratios and 95% confidence intervals.

In additional analyses, provided that the event numbers are sufficient, we will adjust for centre and predefined risk factors (i.e., age, sex, body mass index and the vascular factors presented in Table 1). Hypothesis tests will be 2-sided using a significance level of 0.05. Statistical analysis will be performed using Stata (StataCorp, College Station, TX).

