#### **FIGURE LEGENDS**

Figure 1. Flow of patients (see page 2)

Figure 2: Kaplan-Meier curves of cumulative probability of any stroke during follow-up, according to treatment group (intention-to-treat population)

Log-rank test is used to test the hypothesis that the cumulative incidence of stroke is the same in the two groups.

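### Figure 2 presents Kaplan-Meier curves that censor non-stroke death as the cumulative probability of stroke, which overstates absolute risk, and its log-rank note names the wrong hypothesis

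*SAP*

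**What the plan says.** The primary endpoint in SAP section 3.3 is "Fatal and non-fatal stroke in any arterial territory during trial follow-up". Death from causes other than stroke is not part of it.

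The same section gives one rule for the Cox models, "with patients censored at the time of first event of each type, death, last contact date, or the end of follow-up", and continues: "Kaplan-Meier survival analysis will be used to construct time-to-event curves". The log-rank test is to assess a difference between the arms in cumulative stroke risk. Follow-up runs from 1 year to about 7.5 years.

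The legend of Figure 2 describes "Kaplan-Meier curves of cumulative probability of any stroke during follow-up, according to treatment group", and its note reads "Log-rank test is used to test the hypothesis that the cumulative incidence of stroke is the same in the two groups".

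All-cause mortality, "Death of any cause during follow-up", is a separate secondary endpoint, and Table 3 gives it a hazard ratio. The SAP names no competing-risk estimator.

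**The concern.** A patient who dies of another cause can no longer have a stroke. Kaplan-Meier with that death censored treats the patient as if still able to have one later. Its complement therefore describes a setting without other causes of death, whereas the Figure 2 legend offers it as the probability of stroke in these patients.

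Two statements in the plan then fail. The curve is not the cumulative probability the legend promises, because it is too high once stroke-free patients die while strokes still occur. And a log-rank test with those deaths censored addresses equal cause-specific hazards of stroke, not equal cumulative incidence as the note says.

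At stake is any absolute stroke risk read from the figure, above all in the long tail, and with it the visible gap between the arms.

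The censoring sentence is also loosely drafted. It lists the endpoint's own first event, and death, among the censoring times and never says what counts as the event.

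**Working it through.** **Inputs from the SAP (section 3.5).** Medical-arm stroke risk is 12% in year 1, 7% in year 2 and 5% in year 3. The assumed risk reduction with stenting is 45%.

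**Assumptions, not in the SAP.** Stroke risk stays at 5% a year after year 3. Non-stroke death is 2%, 4% or 6% a year, equal in both arms. A hazard ratio of 0.55 approximates the 45% reduction. Hazards are constant within each year.

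**Step 1: the plan's own figure.** The stated 3-year risk of 24% is the simple sum 12 + 7 + 5. Compounded as a survival curve would do it, the risk is 1 − 0.88 × 0.93 × 0.95 = 0.2225, or 22.3%. This is what one minus Kaplan-Meier estimates at 3 years with death censored.

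**Step 2: the same at 7.5 years.** 1 − 0.88 × 0.93 × 0.95^5.5 = 0.3828, or 38.3%.

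**Step 3: cumulative incidence with death competing.** Let s = −ln(1 − yearly stroke risk), d = −ln(1 − yearly death risk), and S the proportion alive and stroke-free at the start of the interval. Over an interval of length t years the cumulative incidence rises by

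S × s/(s + d) × (1 − exp(−(s + d)t)),

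and S is then multiplied by exp(−(s + d)t).

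Worked example at 4% deaths a year (d = 0.0408):
- Year 1: s = 0.1278, increment 0.1176, S becomes 0.88 × 0.96 = 0.8448.
- Year 2: s = 0.0726, increment 0.0580, S becomes 0.7542.
- Year 3: s = 0.0513, increment 0.0370, so the 3-year total is 0.2126.
- Continued to 7.5 years, the total is 0.3425.

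**Results, medical arm:**

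| Non-stroke death per year (assumed) | 3 y: 1 − KM | 3 y: cumulative incidence | Excess (points) | 7.5 y: 1 − KM | 7.5 y: cumulative incidence | Excess (points) |
|---|---|---|---|---|---|---|
| 2% | 22.3% | 21.8% | 0.5 | 38.3% | 36.2% | 2.1 |
| 4% | 22.3% | 21.3% | 1.0 | 38.3% | 34.3% | 4.0 |
| 6% | 22.3% | 20.8% | 1.5 | 38.3% | 32.5% | 5.8 |

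Over a wider range of 1% to 8% deaths a year, the excess is 0.3 to 2.0 points at 3 years and 1.1 to 7.5 points at 7.5 years.

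**Step 4: gap between the arms.** At 7.5 years, one minus Kaplan-Meier is 38.3% against 23.3%, a gap of 15.0 points. By cumulative incidence the gap is 14.2 points at 2% deaths a year and 12.9 points at 6%, so it is overstated even with equal mortality in the two arms.

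**The case against.** The strongest reply is that nothing inferential is wrong, and that stands. Censoring non-stroke death is valid for a cause-specific hazard ratio and its log-rank test. Table 3 reports patient counts over person-months with a hazard ratio and P value, none of which the Kaplan-Meier complement inflates.

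The bias is also small beside sampling error. With 182 patients, and assuming about 91 per arm, a 22.25% risk has a simple binomial standard error of √(0.2225 × 0.7775/91) = 0.044, so a 95% interval of about ±8.5 points, ignoring censoring. That limits the importance of the point but does not make the label right: the error always runs upward and is avoidable at almost no cost.

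Four stronger readings are tempting, and the SAP does not support them.

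- *Deaths would drop out of the all-cause death analysis.* Read literally, the sentence would censor every endpoint's own event and leave nothing to analyse, so it can only mean that time at risk ends there. For all-cause death, or a fatal stroke, the death is the event, and Table 3 plans a hazard ratio for death. This is loose drafting, not a planned loss of events.
- *The rule governs every endpoint.* It belongs to the Cox models. For the short-term outcomes, "The proportions of outcome events within 30-days of treatment will be compared with exact logistic regression", and costs and quality-adjusted life years are referred to the protocol.
- *A risk difference or number needed to treat will be wrong.* The SAP plans neither. The risk is confined to what readers take from the figure.
- *The 7.5-year excess is the typical error.* Only the first recruited patients are followed that long, and the last recruited have 1 year.

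**Conclusion.** The point holds for the stroke time-to-event endpoints and is confined to the absolute-risk display and the wording around it. As written, Figure 2 would overstate the cumulative probability of stroke, its note misnames the hypothesis the log-rank test addresses, and the censoring sentence needs redrafting.

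The direction is certain once any stroke-free patient dies of another cause while strokes still occur. The size is not, because the SAP gives no non-stroke death rate and no stroke risk beyond year 3. Under the stated assumptions the medical-arm curve is about 0.5-1.5 points too high at 3 years and 2-6 points at 7.5 years. If non-stroke mortality is low, the error is modest. If it differs by arm, the gap between the curves would depart further from the gap in actual risk. The change is worth making, but it does not alter the trial's primary comparison.

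**What to change.** 1. Draw Figure 2, and report any absolute stroke risks, as Aalen-Johansen cumulative incidence by arm with non-stroke death as a competing event. Name the estimator in the legend.
2. Keep the Cox hazard ratio and the log-rank test, and label both cause-specific. Reword the Figure 2 note so that the hypothesis tested is *equal cause-specific hazards of stroke*. Without this, the new figure would carry a P value for a hypothesis about the curves that the test does not address. Align the log-rank sentence in section 3.3 in the same way.
3. Redraft the censoring sentence in section 3.3, for example: *The first event of the type analysed counts as the event, including fatal stroke for the stroke endpoint and death for the all-cause death endpoint. Patients without that event are censored at last contact or end of follow-up and, in the cause-specific Cox and log-rank analyses of stroke, at non-stroke death.*

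The cost is a few sentences in the SAP and one routine competing-risks procedure in Stata. The downside is small: slightly lower reported absolute risks and a little extra analysis work. No hazard ratio, test or count in Table 3 changes.

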# Statistical Analysis Plan (SAP) for Vertebral artery Ischaemia Stenting Trial (VIST)

# 1. SHORT DESCRIPTION OF PROJECT

Does vertebral artery stenting prevent recurrent stroke in symptomatic vertebral artery stenosis?

See VIST clinical study protocol Version 8.0 (10th June 2014) for details.

VIST is an international multicentre randomised controlled trial with the main aim to investigate the risks and benefits of vertebral angioplasty and stenting plus best medical treatment for symptomatic vertebral stenosis compared with best medical treatment alone. The efficacy is determined for the cohort as a whole and for extracranial and intracranial vertebral stenosis separately.

From an analytic point of view, we are treating VIST as a non-inferiority or equivalence trial, that is, a trial aimed to determine whether stenting is as good as best medical therapy alone in preventing recurrent stroke in patients with vertebral artery stenosis.

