# 4. PROPOSED TABLES AND FIGURE LEGENDS

Table 1. Baseline characteristics of patients enrolled into the VIST, according to treatment group (intention-to-treat population) (per protocol data will be presented in columns to the right or in a separate similar table)

Characteristic a	Best medical treatment	Angioplasty/stenting	P value b
	group (n = xx)	group (n = xx)	
Age (years)			
Male, n (%)			
Body mass index c			
Vascular risk factors			
Treated hypertension			
Treated hyperlipidaemia			
Previous myocardial infarction			
Angina in last 6 months			
Peripheral artery disease			
Atrial fibrillation			
Qualifying event			
TIA			
Non-disabling stroke d			
Location of vertebral artery target			
stenosis			
Extracranial (V1 to V3)			
Intracranial (V4)			
Modified Rankin Score			

TIA, transient ischemic attack; VIST, Vertebral artery Ischaemia Stenting Trial.

a Values are number (%) of patients or mean (± SD).

b Treatment groups are compared using Fisher's exact test or *t* tests.

c BMI is calculated as weight (kg) divided by height (m) squared.

d Modified Rankin scale score  $\leq$ 3 at inclusion.

Table 2. Medica	l treatment and b	ood pressure	and risk factor	control over th	ne first 30 days over

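### Target-stenosis location is the SAP's own efficacy split, but no analysis of the pooled stroke effect stratifies by it or adjusts for it; stratifying would cost almost nothing

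*SAP*

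**What the plan says.** Section 1 sets two levels of inference: "The efficacy is determined for the cohort as a whole and for extracranial and intracranial vertebral stenosis separately". Table 3 follows this, giving extracranial and intracranial target stenosis their own rows under the primary endpoint.

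For the pooled comparison, section 3.3 states that, if event numbers suffice, "hazard ratios with 95% confidence intervals will be estimated by using Cox proportional hazards regression models", and that "the log-rank test will be used to evaluate whether there is a statistical significance difference in the cumulative risk of stroke" between the arms. No stratum or covariate is named for either. The Figure 2 legend repeats a plain log-rank test.

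The adjusted model is introduced with "In additional analyses, provided that the event numbers are sufficient", and its covariates are fixed: "we will adjust for centre and predefined risk factors (i.e., age, sex, body mass index and the vascular factors presented in Table 1". In Table 1 the vascular risk factors are six items: treated hypertension, treated hyperlipidaemia, previous myocardial infarction, angina, peripheral artery disease and atrial fibrillation. Location of the target stenosis stands under a separate heading, so on a plain reading it is not in the adjusted model.

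**The concern.** The SAP singles out one baseline factor as important enough for separate efficacy estimates. It then leaves that factor out of every model of the overall effect, while adjusting for body mass index and angina.

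Table 1 will print location by arm with a P value. If the arms turn out to differ, no prespecified pooled analysis responds to the difference, and any correction would be chosen after seeing the data. The adjusted model does not help: it omits location, and it may not be run at all, since it carries nine covariates plus centre and depends on event numbers.

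At stake is how well the headline hazard ratio can be read given the imbalance actually observed, in a trial that enrolled 182 patients against 540 planned. The validity of the test is not at stake.

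**Working it through.** **1. The plan's own sample size (section 3.5).** Inputs: 80% power, two-sided 5%, 3-year control risk 24%, risk reduction 45%. Freedman's formula with hazard ratio 0.55 needs 94 events. The stented-arm risk is 1 − 0.76^0.55 = 0.140, so the mean risk is (0.240 + 0.140)/2 = 0.190 and N = 94/0.190 ≈ 495, against the stated 490. Then 490 × 1.1 = 539, stated as 540. The design figures therefore reproduce.

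**2. Information at N = 182.** Assume 91 per arm and 3-year risks of 24% and 24% × 0.55 = 13.2%. Expected events are 91 × (0.240 + 0.132) ≈ 34, and SE(log HR) ≈ 2/√33.85 = 0.34. Actual follow-up runs from 1 to about 7.5 years, so the true count may differ.

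**3. Size of a chance imbalance.** The SAP gives neither the intracranial share f nor the intracranial-to-extracranial hazard ratio r. Assumed ranges are f = 10% to 40% and r = 1.5 to 3, with simple 1:1 randomisation that does not balance location.

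- SD of the between-arm difference in share = √(f(1 − f) × 2/91)
- Multiplier on the pooled HR ≈ (1 + a(r − 1))/(1 + b(r − 1)), where a and b are the shares in the two arms, placed symmetrically about f

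Example with f = 20%, r = 2: SD = √(0.16 × 2/91) = 5.9 points. At 1 SD, a ≈ 0.230 and b ≈ 0.170, giving 1.230/1.170 ≈ 1.05.

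| f | SD (points) | r = 1.5: 1 SD / 1.96 SD | r = 2: 1 SD / 1.96 SD | r = 3: 1 SD / 1.96 SD |
|---|---|---|---|---|
| 10% | 4.4 | 1.021 / 1.042 | 1.041 / 1.083 | 1.077 / 1.157 |
| 20% | 5.9 | 1.027 / 1.054 | 1.051 / 1.102 | 1.088 / 1.181 |
| 30% | 6.8 | 1.030 / 1.060 | 1.054 / 1.108 | 1.089 / 1.182 |
| 40% | 7.3 | 1.031 / 1.061 | 1.053 / 1.107 | 1.084 / 1.172 |

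The shift can go either way. Against the SE of 0.34, the 1.96-SD shifts run from ln(1.042)/0.344 = 0.12 to ln(1.182)/0.344 = 0.49 of one SE.

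**4. What stratifying does.** Simulation with 3,000 trials per scenario, n = 182 and 3 years of follow-up. Scenarios were (f, r) = (20%, 2), (20%, 3) and (40%, 2), each under the null and under HR 0.516 = ln(0.868)/ln(0.76), and each with and without allocation balanced by location.

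| | Unstratified | Stratified by location |
|---|---|---|
| Type I error | 4.5% to 5.1% | 4.7% to 5.6% |
| Power at HR 0.516 | 43% to 47% | 45% to 47% |
| Median HR when the true HR is 0.516 | 0.515 to 0.520 | 0.507 to 0.515 |

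Monte Carlo error on a 5% rate is √(0.05 × 0.95/3000) ≈ 0.4 points, so the type I error rates are not distinguishable from 5%. Under simple randomisation, stratifying moved the log HR by an SD of about 0.06 (r = 2) or 0.09 (r = 3), against a sampling SD of about 0.31 under the null.

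**The case against.** A reader might infer that the primary analysis is biased, or that its P value is wrong when location is unbalanced. The documents do not support that. Chance imbalance under randomisation is part of the sampling error that the confidence interval and P value already cover, and the simulated unstratified test keeps its 5% level. A hazard ratio averaged over locations is also a legitimate target.

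A reader might also infer that location is ignored altogether. It is not. Table 1 shows it by arm and Table 3 plans hazard ratios within each location, which are free of imbalance between locations. What is missing is one pooled estimate that combines the within-location comparisons.

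Two premises are also outside the SAP. It does not say that location predicts stroke risk; planning separate efficacy estimates does not establish different baseline hazards. Nor does it describe the randomisation scheme, which is properly left to the protocol. If allocation was stratified by location, the imbalance argument largely disappears.

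Finally, it is tempting to ask for qualifying event (TIA or stroke) in the adjusted model as well. Nothing in the SAP shows a need for it, and nine covariates plus centre is already crowded for about 34 events.

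All of this stands, and it limits the point to prespecification and a small gain in efficiency. It does not remove the point. The omission is in the SAP's own text, and the remedy is the same under either randomisation scheme: stratifying matches the analysis to the design if location was balanced, and deals with imbalance if it was not.

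**Conclusion.** The point holds as a modest one. Location is the SAP's main efficacy split, yet neither the pooled log-rank test, nor the pooled Cox model, nor the adjusted model uses it. The planned test is valid.

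The possible shift in the pooled hazard ratio is about 2% to 9% for a 1-SD imbalance and about 4% to 18% for a 1.96-SD imbalance, at most about half of one standard error. Those figures rest on assumed values for the intracranial share and the relative hazard, on 91 patients per arm, on about 34 events at the design rates, and on randomisation that did not balance location. If location is not prognostic, or was balanced by design, the shift is close to nil. The gain in power is about 0 to 2 points. The reason to act is that the improvement is almost free and can be prespecified only before the results are seen.

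**What to change.** Before unblinding, in section 3.3 and the Figure 2 legend:

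- Make the whole-cohort log-rank test and Cox model stratified by target-stenosis location, extracranial (V1-V3) versus intracranial (V4), as recorded at baseline.
- Keep the unstratified log-rank test and hazard ratio as a sensitivity analysis.
- Leave the covariate list of the adjusted model as it is.

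The cost is a few words in the SAP and a strata option in the code. Location is already a Table 1 variable, and a stratified Cox model estimates no extra coefficient. The reported hazard ratio becomes a within-location effect, which in the simulations lay slightly further from 1 than the unstratified one; one sentence in the SAP should say so.

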# Table 4. Serious adverse events within the first 30 days (intention-to-treat population)

CI, confidence interval; mRS, modified Rankin Scale; OR, odds ratio; TIA, transient ischemic attack.

ANALYSIS OF ANGIOGRAPHIC IMAGING DURING					
STENTING					
	Pre-Stenting	Immediate post-stenting			
Angiographic stenosis	? mean (SD)	? mean (SD)			
REPEAT NON-INVASIVE IMAGING AT 1 YEAR					
	At randomisation	At 1 year			
No. (%) with stenosis ≥50%					
Angioplasty/stenting					
Best medical therapy					
REPEAT NON-INVASIVE IMAGING AT 1 YEAR No. (%) with stenosis ≥50% Angioplasty/stenting Best medical therapy	At randomisation	At 1 year			

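### The 30-day between-arm odds ratio starts the clock differently by arm and by whether stenting took place, so it does not compare the randomised groups over the same period, and the bias can go either way

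*SAP*

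**What the plan says.** SAP Section 3.3 sets two kinds of clock. For the 3-month and complete follow-up analyses, "follow-up will start immediately after randomisation" in both arms. The short-term analysis has a different purpose: "We will also analyse short term outcomes to assess the operative risk". Its 30-day clock starts "immediately after recruitment for patients allocated medical treatment alone and immediately after the stenting procedure for patients allocated stenting". A further rule covers the remainder: "If stenting was not performed in a patient allocated stenting, follow-up will begin directly after randomisation".

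The result is used as a between-arm contrast: "The proportions of outcome events within 30-days of treatment will be compared with exact logistic regression", giving odds ratios with 95% confidence intervals. Table 4 shows them by allocated group and is labelled as an intention-to-treat table.

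The length of the window is left open. The SAP says that "this may be adjusted before unblinding to results and analysis if we find stenting has not been carried out by 30 days" for a sizeable number of patients. It does not say how long the wait for stenting was or was expected to be, or how often a planned procedure did not go ahead.

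**The concern.** There are three starting rules: recruitment (medical arm), the end of the procedure (stented patients) and randomisation (allocated stenting, never stented). Even if recruitment and randomisation mean the same day, two problems remain.

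- The arms are observed over different periods. The medical arm contributes the first 30 days after entry. Stented patients contribute a later 30 days.
- Within the stenting arm, the clock is chosen by a post-randomisation event, and that event may itself be caused by the outcome. A patient who has a stroke while waiting and is then stented does not have that stroke counted. A patient whose stroke during the wait leads to cancellation does. A patient who dies while waiting is never stented, so a death within 30 days of randomisation counts.

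An odds ratio formed this way is not protected by randomisation, although the intention-to-treat label tells the reader that it is. At stake is the early between-arm comparison of stroke and death in Table 4, where few events are expected and one or two misplaced events would matter.

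**Working it through.** The SAP gives no figure for this rule, so there is none to reproduce. The question is what odds ratio the rule would give if stenting had no effect at all.

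**Inputs from the SAP.** Year-1 stroke risk 12% (Section 3.5), so the year-1 cumulative hazard is −ln(0.88) = 0.1278. Enrolled: 182 (Section 3.5).

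**Assumptions (not in the SAP).**
- The same risk applies in both arms, with no added procedural risk.
- Recruitment and randomisation fall on the same day.
- Either 25% or 50% of the year-1 cumulative hazard falls in days 0-30, with an exponentially declining hazard; a flat hazard is the comparison case.
- Stenting takes place on day w = 14 or 30.
- A share c of patients with a stroke during the wait have stenting cancelled; everyone else allocated stenting is stented.
- A waiting stroke does not change later risk.

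**Formulas.** Let H(t) = K(1 − e^(−t/τ)). The 25% case has τ = 108.6 days and K = 0.1324; the 50% case has τ = 43.3 days and K = 0.1279.

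- Medical arm, days 0-30: pM = 1 − exp(−H(30))
- Stroke during the wait: pW = 1 − exp(−H(w))
- 30 days after the procedure: pS = 1 − exp(−[H(w+30) − H(w)])
- Stenting arm as the SAP would count it: pS + c·pW·(1 − pS)
- Share c at which the null odds ratio is 1: (pM − pS) / [pW(1 − pS)]

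**One row in full (50%, w = 30).** H(30) = 0.0639 and H(60) = 0.0959.
- pM = pW = 0.0619, and pS = 1 − exp(−0.0320) = 0.0315.
- With c = 0: OR = (0.0315/0.9685) / (0.0619/0.9381) = 0.0325/0.0660 = 0.49.
- With c = 1: the stenting arm is 0.0315 + 0.0619 × 0.9685 = 0.0914, and OR = 0.1006/0.0660 = 1.52.

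**All rows.**

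| Share of year-1 hazard in 30 days | Wait (days) | pM | pW | pS | Null OR, c = 0 | Null OR, c = 1 | c giving OR = 1 |
|---|---|---|---|---|---|---|---|
| 25% | 14 | 3.15% | 1.59% | 2.77% | 0.88 | 1.39 | 0.24 |
| 25% | 30 | 3.15% | 3.15% | 2.40% | 0.76 | 1.78 | 0.24 |
| 50% | 14 | 6.19% | 3.47% | 4.52% | 0.72 | 1.29 | 0.50 |
| 50% | 30 | 6.19% | 6.19% | 3.15% | 0.49 | 1.52 | 0.51 |
| flat hazard | 14 | 1.04% | 0.49% | 1.04% | 1.00 | 1.47 | 0 |
| flat hazard | 30 | 1.04% | 1.04% | 1.04% | 1.00 | 2.01 | 0 |

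**In events.** With equal allocation (an assumption), 182/2 = 91 per arm. In the declining-hazard rows the medical arm expects 91 × 3.15% = 2.9 to 91 × 6.19% = 5.6 strokes. If no waiting stroke cancels stenting, 91 × 1.59% = 1.4 to 91 × 6.19% = 5.6 strokes in the stenting arm go uncounted. That is the upper bound; the number falls as c rises.

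With both arms started at randomisation and given the same window, the null odds ratio is 1.00 by construction.

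**The case against.** The strongest defence is that a window anchored to the procedure is a sensible way to describe operative risk, which is the stated aim. The SAP already has a clean short-term contrast in stroke at 3 months from randomisation, and it also lists stroke or death within 30 days of the procedure as a secondary endpoint. Adverse events are presented by arm separately (Section 3.4). All of this stands, and it limits the severity. It does not rescue the odds ratio: a procedure-anchored window suits a description of the stenting arm, not a contrast with a group that had no procedure.

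A reader might infer several stronger things that the SAP does not support.

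- **That the bias favours stenting.** This follows only if risk falls after entry and few waiting strokes lead to cancellation. The rule for never-stented patients pulls the other way, and it captures deaths during the wait.
- **That a flat hazard removes the bias.** It does so only when no waiting stroke cancels stenting; otherwise the null odds ratio exceeds 1.
- **That strokes during the procedure are excluded.** Starting after the procedure does say this literally. However, the aim is operative risk, Table 4 has a row for serious adverse events related to the operation, and Table 3 counts periprocedural stroke. These events are evidently meant to count, so this is a point of wording.
- **That the option to change the 30 days contradicts the rule or must be deleted.** Late stenting is relevant, since the medical arm and never-stented patients do run from randomisation. The change is allowed only before unblinding and is triggered by procedure timing, not outcome. What can be said is that changing the length of the window would not align the starting points.

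**Conclusion.** The concern holds as a defect in the design of the 30-day odds ratio. The choice of clock in the stenting arm depends on a post-randomisation event, so the contrast does not match its intention-to-treat label.

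Neither the direction nor the size of the bias can be fixed from the SAP. Under the declining-hazard assumptions above, the null odds ratio ranges from 0.49-0.88 (no waiting stroke cancels stenting) to 1.29-1.78 (all do). It crosses 1 when about a quarter to a half of waiting strokes cancel the procedure. The waiting time, the early hazard and the cancellation share are all assumed; only the 12% year-1 risk and the 182 patients come from the document.

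The primary, 3-month and full follow-up analyses start at randomisation in both arms and are unaffected. Severity is moderate.

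**What to change.** Separate the two questions that the present rule combines.

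1. **Between-arm short-term comparison (Table 4).** Start at randomisation in both arms, analyse by allocated group, and use one common window: either 30 days or the SAP's existing 3 months. Fix the choice before unblinding. Exact logistic regression can stay.
2. **Operative risk.** Report a one-arm proportion with an exact 95% confidence interval in patients in whom stenting was attempted. Count from the start of the procedure, so that events during it clearly count, to day 30. Give no odds ratio against the medical arm.

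The cost is a change of wording and one re-specified table. The stenting and endpoint forms listed in Section 2 are already collected, so no new data collection should be needed. The downside is that a 30-day window from randomisation may not cover the full 30 days after a late procedure. A 3-month window covers more of them, but it dilutes the 30-day contrast and, for stroke, repeats a row already in Table 3. The separate operative-risk report limits what is lost either way.
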